1.2 Scope of the statistical analysis plan

This SAP is based on the NN1250-4252 protocol version 3.0.

CONFIDENTIAL

Date: Version: Status: Page:

2 Statistical considerations

2.1 General considerations

The in-trial period will include information collected at or after the date of randomisation and until the date of:

- The last scheduled subject-site contact
- Withdrawal for subjects who withdraw their informed consent
- The last subject-investigator contact as defined by the investigator for subjects who are lost to follow-up
- Death for subjects who die before any of the above

The on-treatment period represents the time period in which a subject is considered exposed to trial product. The period starts on day of the first dose of trial product and ends 7 days after last dose of trial product is taken, but no later than the end of the in-trial period.

Maintenance period 1 starts on the day of V18/V18A. For subjects not attending neither V18 nor V18A, but still in trial for more than 16 weeks, maintenance 1 instead starts 16 weeks (112 days) after randomisation.

Maintenance period 2 starts at the date of V57/V57A. Subjects not attending neither V57 nor V57A will not have a maintenance 2 period, regardless of duration in trial.

A subject is completing the trial if he/she attends V93 or V93A at the end of maintenance 2 period. It is considered completing trial on treatment if the subject attends V93 without premature discontinuation of trial product.

All efficacy endpoints will be summarised using the full analysis set (FAS) and safety endpoints excluding hypoglycaemic endpoints will be summarised using the safety analysis set (SAS). For hypoglycaemia, the SAS will be used when on-treatment data is used, and FAS is used for in-trial data.

All statistical analysis of efficacy and safety endpoints will be based on the FAS unless otherwise specified. Confirmatory analysis addressing the primary estimand will include on-treatment data and not available retrieved (V93A) data.

The primary objective is to compare the effects of IDeg OD and IGlar 300 U/mL OD on the rate of hypoglycaemia in subjects with type 2 diabetes mellitus, inadequately treated with basal insulin with or without oral anti-diabetic drugs. The primary estimand is the treatment difference between IDeg and IGlar 300 U/mL assuming that all randomised subjects adhered to the randomised treatment, and is thus referred as the on-treatment estimand. The on-treatment estimand addresses the treatment difference for subjects who can be long-term treated with either of the two insulins.

CONFIDENTIAL

Date: Version: Status: Page:

Data collected after premature treatment discontinuation will not be used when addressing the ontreatment estimand. With the aim of comparing a safety endpoint this estimand is considered the most relevant as it compares the occurrence of a safety endpoint that is caused by the drug during exposure to the drug. The confirmatory endpoints will additionally be investigated with a ITT estimand.

The secondary estimand is the treatment difference between IDeg and IGlar 300 U/mL regardless of whether subjects adhered to the randomised treatment throughout the trial, that is an ITT estimand. For this ITT estimand, data collected after premature discontinuation will be used.

In accordance with guidance⁹ endpoints will be assessed at frequent visits and also for subjects who prematurely discontinue treatment. When an assessment is planned at randomisation visit, this value will be used as baseline value. If this value is missing the last recorded value before randomisation visit will be used. For assessments planned only at screening, the screening values will be used as baseline. If this value is missing, the first recorded visit after screening, but no later than the day of randomisation, will be used.

For patients not initiating maintenance period 2 on treatment a summary table of reasons for treatment discontinuation will be reported.

The severe hypoglycaemia episodes included in the statistical analysis are all events adjudicated with the outcome severe hypoglycaemia.

Laboratory values below the lower limit of quantification (LLOQ) will be set to ½LLOQ. Laboratory values above the upper limit of quantification (ULOQ) will be set to ULOQ+1.

The primary and secondary endpoints will be tested in a hierarchical order using the on-treatment estimand to control the family wise Type I error in the strong sense. Presentation of results from a statistical analysis will include the estimated treatment means as well as estimated mean treatment difference (or ratio) together with the two-sided 95% confidence interval and corresponding two-sided p-value.

In the statistical models explanatory factors will be categorized as follows:

- 1. Treatment: IDeg, IGlar 300 U/mL
- **2.** Pre-trial 0 OADs, 1OAD, \geq 2 OADs
- 3. Region: Europe, North America
- 4. Sex: male, female
- 5. Dosing time: morning, evening

2.2 **Power calculation**

The power is based on the primary objective and the primary endpoint, number of hypoglycaemic episodes during maintenance treatment.

For the power calculations it is assumed that the true treatment rate ratio (RR) is 0.75 corresponding to a 25% reduction in rate of hypoglycaemia in maintenance period with IDeg OD compared to

Statistical Analysis Plan Trial ID: NN1250-4252 UTN: U1111-1184-8175 EudraCT No.: 2016-002801-20	CONFIDENTIAL	Date: Version: Status: Page:	12 March 2019 3.0 Final 11 of 31	Novo Nordisk
---	--------------	---------------------------------------	---	--------------

IGlar 300 U/mL OD. Sample size is determined based on a negative binomial model with log-offset equal to exposure time in maintenance. The observed rate of severe or BG confirmed symptomatic hypoglycaemia for IDeg is assumed to be 1.8 per patient years of exposure (PYE) and the dispersion parameter in the negative binomial distribution is assumed to be 3.1. Furthermore it is assumed that 4% of subjects will withdraw before starting the maintenance period and therefore have no on-treatment data for the maintenance period. For these 4% the treatment ratio is set to 1. Rate assumptions are based on experience from SWITCH 2 (NN1250-3998), which has similar inclusion criteria. Dispersion parameter assumptions are based on experience from the Degludec phase 3a and 3b program. Assumptions concerning withdrawal are similarly based on actual withdrawal rate of the trial during titration and maintenance 1.

The power equals 79% with the number of randomised subjects and the assumptions above.

			Yearly event rate			
		1.5	1.8	2.0		
RR	Adjusted RR	Primary	Primary	Primary		
0.80	0.812	55%	57%	58%		
0.75	0.765	77%	79%	79%		
0.70	0.718	92%	93%	93%		

 Table 2–1
 Power for the on-treatment estimand for combinations of RR and event rates

The marginal power for detecting a difference between IDeg OD and IGlar 300 U/mL OD with 805 subjects per treatment arm assuming a one-sided t-test at the 2.5% significance level for the confirmatory secondary dose endpoints is shown below. The assumptions are based on data from NN1250-3998 with respect to hypoglycaemic episodes and the phase 3a+b program for the dose-difference.

 Table 2–2
 Marginal power for confirmatory secondary endpoints

		Assumptions			
Endpoint	True ratio	Adjusted RR	CV/ Over dispersion	Rate in IDeg treatment arm	Power
Insulin dose (U)	0.90	0.906	0.65	-	92%
Number of nocturnal, severe or BG confirmed symptomatic hypoglycaemic episodes during maintenance 2	0.7	0.718	3.1	0.55	82%
Number of severe hypoglycaemic episodes during maintenance 2	0.6	0.624	3.1	0.03	31%

Statistical Analysis PlanTrial ID: NN1250-4252UTN: U1111-1184-8175EudraCT No.: 2016-002801-20	Date: Version: Status: Page:	12 March 2019 3.0 Final 12 of 31	Novo Nordisk
---	---------------------------------------	---	--------------

2.3 Definition of analysis sets

Full analysis set (FAS): includes all randomised subjects. In exceptional cases, subjects may be eliminated from the full analysis set. In such cases the elimination will be justified and documented. In the statistical evaluation of the full analysis set subjects contribute "as randomised".

Safety analysis set (SAS): includes all subjects receiving at least one dose of the investigational product or comparator. Subjects in the safety set will contribute to the evaluation "as treated".

Randomised subjects who are lost to follow up and where no exposure information of the investigational product or comparators is available after randomisation will be handled as unexposed.

Before data are released for statistical analysis, a review of all data will take place to identify protocol deviations that could potentially affect the results. In exceptional cases a decision to exclude any subject or observation from the statistical analysis can be made. This is the joint responsibility of the members of the study group. The subjects or observations to be excluded, and the reasons for their exclusion must be documented before database lock. The subjects and observations excluded from analysis sets, and the reason for this, will be described in the clinical trial report.

2.4 Primary endpoint

2.4.1 Primary statistical analysis for the on-treatment estimand

The on-treatment estimand will be estimated based on information from maintenance 2 collected when subjects use randomised treatment including a 7-day follow-up period (on-treatment data). Subjects that discontinue randomised treatment during maintenance 2 will contribute with the available on treatment data from maintenance 2. For subjects that discontinue randomised treatment during the titration period or maintenance 1, the number of events in maintenance 2 will be imputed based on data from the same arm from maintenance 2 for subjects that discontinued randomised treatment during maintenance 2. Missing data within each group will be imputed as follows:

- First 1000 samples from the posterior distribution of model parameters will be extracted. The model will be fitted to the on-treatment maintenance 2 data for subjects that discontinued randomised treatment during maintenance 2. This will be done using a Bayes Poisson log-link model dosing time as a factor, age as covariate, and log of exposure time as offset.
- For each sample of model parameters, the total number of hypoglycaemia events for subjects that discontinued randomised treatment in the titration period or maintenance 1 will be imputed as a random number of events from a Poisson distribution using the sampled parameters.

CONFIDENTIAL

Date: Version: Status: Page: 12 March 2019 Novo Nordisk 3.0 Final 13 of 31

Having 1000 complete data sets that have maintenance 2 data for all randomised subjects, the mean treatment ratio will be estimated using a negative binomial model with all the factors described in section 2.1, age as covariate and log exposure time as offset. The estimates and standard deviations will be pooled to one estimate and associated standard deviation using Rubin's formula. From these the 95% confidence intervals for the treatment ratio and the associated p-value will be calculated.

If the above imputation model cannot fit or leads to inflate the standard error of the treatment ratio on logscale by more than 15% compared to a negative binomial model fitted to the available ontreatment data during maintenance 2 without any imputation, an alternative model is used for the analysis: The imputation model will be a negative binomial model fitted to all available ontreatment data during maintenance 2 and including all factors described in section 2.1, age as covariate and log exposure time as offset. If this model cannot fit either, the imputation model is fit as a Poisson model to all available on-treatment maintenance 2 data, and if needed factors are left out from the imputation model in the following order:

- sex
- region
- previous OAD treatment

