2.4.2 Sensitivity analyses for the on-treatment estimand

To investigate missing not at random scenarios, a tipping point analysis of the hypothesis that IDeg is superior to IGlar 300 U/mL will be performed for the on-treatment estimand. In this analysis the event rates for subjects that discontinued randomised treatment in the IDeg OD arm during either titration or maintenance 1 periods is gradually increased until the difference between the two treatments is no longer statistically significantly different. If the penalty found by this method is evaluated to be clinically plausible the sensitivity analysis does not support the primary analysis. If the penalty is not considered plausible the sensitivity analysis supports the primary analysis.

To investigate the potential influence of subjects with high number of events, the analysis of the ontreatment estimand will be repeated on data where the maximal number of events in maintenance 2 is truncated at three. The value three is based on data from SWITCH 2 (NN1250-3998) where three hypos correspond to the 95% percentile in the IDeg arm. Furthermore, a statistical sensitivity analysis is performed with a truncation at seven, to accommodate for the longer analysis period in the current trial (36 weeks instead of 16 weeks).

The primary analysis will be performed using only available on-treatment data during maintenance 2. Subjects without on-treatment data for maintenance 2 period will be excluded from this analysis, and thus no imputation is needed.

The primary analysis will be repeated, but considering the full maintenance period (maintenance 1 and maintenance 2). Missing data will be imputed for subjects that discontinued randomised treatment during titration period only, using on-treatment data for maintenance 1 and 2. This

Statistical Analysis Plan Trial ID: NN1250-4252 UTN: U1111-1184-8175 EudraCT No.: 2016-002801-20	CONFIDENTIAL	Date: Version: Status: Page:	12 March 2019 3.0 Final 14 of 31	Novo Nordisk
---	--------------	---------------------------------------	---	--------------

analysis evaluates if including the data from the discontinued BG-meter challenge the overall conclusion of the trial.

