2.5 Secondary endpoints

2.5.1 Confirmatory secondary endpoints

Provided that IDeg OD is superior to IGlar 300 U/mL OD for the primary endpoint using the ontreatment estimand, the confirmatory secondary endpoints will be tested for superiority of IDeg OD over IGlar 300 U/mL OD using the on-treatment estimand.

The confirmatory secondary endpoints are given below; the order of the endpoints defines the testing sequence. The hierarchical testing strategy will control the family wise type 1 error in the strong sense at 5% (two sided).

Trial ID: NN1250-4252 CONFIDENTIAL Version: 3.0 UTN: U1111-1184-8175 Status: Final EndraCT No : 2016-002801-20 Page: 15 of 31	Statistical Analysis Plan Trial ID: NN1250-4252 UTN: U1111-1184-8175 EudraCT No : 2016-002801-20	CONFIDENTIAL	Date: Version: Status: Page:	12 March 2019 3.0 Final 15 of 31	Novo Nordisk
---	---	--------------	---------------------------------------	---	--------------

- 1. Basal insulin dose (U) at end of maintenance 2 (up to 88 weeks)
- 2. Number of nocturnal, severe or BG confirmed symptomatic hypoglycaemic episodes during maintenance 2 (36 weeks)
- 3. Number of severe hypoglycaemic episodes during maintenance 2 (36 weeks)

The hypoglycaemic endpoints will be analysed with the same analysis method as the primary endpoint including backup strategy and with similar sensitivity analysis.

Basal insulin dose at end of maintenance 2 will be analysed as follows: A basal insulin dose at every titration, maintenance and end of treatment visit mentioned in the flow chart will be calculated as a mean of the insulin doses in the 7 day period before the visits. For the on-treatment estimand these doses will be analysed on log-scale with an MMRM with the factors described in section 2.1 and age at baseline and logarithm of pre-trial insulin dose as covariate, all nested within visit. If this model does not converge visits and/or factors will be excluded from the analysis. Before transforming to log-scale, dose values of 0 will be assigned the value 0.5.

Insulin dose will also be analysed with the ITT estimand, i.e. including insulin dose collected after premature discontinuation. This is done using a pattern mixture model using multiple imputation to handle missing data. Imputation of missing data at end of trial will be done within the 4 groups of subjects defined by randomised treatment and whether subjects discontinued randomised treatment or not. Missing data within each group will be imputed as follows:

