described in section 2.1, age as covariate and log exposure time as offset. The estimates and standard deviations will be pooled to one estimate and associated standard deviation using Rubin's formula. From these the 95% confidence intervals for the treatment ratio and the associated p-value will be calculated.

If the above imputation model cannot fit or leads to inflate the standard error of the treatment ratio on logscale by more than 15% compared to a negative binomial model fitted to the available ontreatment data during maintenance 2 without any imputation, an alternative model is used for the analysis: The imputation model will be a negative binomial model fitted to all available ontreatment data during maintenance 2 and including all factors described in section 2.1, age as covariate and log exposure time as offset. If this model cannot fit either, the imputation model is fit as a Poisson model to all available on-treatment maintenance 2 data, and if needed factors are left out from the imputation model in the following order:

- sex
- region
- previous OAD treatment

,,

Rationale:

Due to a low number of subjects discontinuing treatment during maintenance 2, the imputation model specified in the protocol is unstable and leads to an extreme number of imputed hypos in several instances (subjects having in the magnitude of millions or billions of hypos in a 36 week period). The instability of the model persists when the simplest imputation model, containing only dosing time and age as factors/covariates, is applied. To ensure the scientific integrity in the reality of sparse data the imputation model is simplified.

In case the subjects discontinuing treatment during maintenance 2 is far from equally distributed across the trial arms, there is a risk that also the simplified Poisson imputation leads to unstable results. As the backup model in the original protocol has proven not always to be able to fit, an alternative is introduced for the on-treatment estimands with imputations.

3.8 Clarification of handling of treatment emergent hypoglycaemic episodes during follow-up period

After p. 88 l. 2179 is added:

"For both periods, hypoglycaemic episodes during the 7 days treatment-emergent period after last drug day will be included."

CONFIDENTIAL

Rationale:

Clarification to align with project derivation rules.

3.9 Sensitivity analyses for primary analysis on-treatment estimand:

p.85 after l. 2092 is added:

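### Poisson imputation makes the primary confidence interval too narrow: the nominal 5% test runs at about 5–8%, depending on an undisclosed number of donors

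*SAP*

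**What the plan says.** In SAP 2.4.1, subjects who stop randomised treatment during titration or maintenance 1 have their maintenance 2 count imputed. The imputation model is a Bayesian Poisson regression on dosing time and age. It is fitted to same-arm subjects who stopped during maintenance 2 (the donors). Each missing count is then "imputed as a random number of events from a Poisson distribution using the sampled parameters". The completed data sets are analysed with a negative binomial model and pooled by Rubin's rules.

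Protocol version 3.0, section 17.4.1, had imputed from a negative binomial model. SAP 3.7 explains the change: "Due to a low number of subjects discontinuing treatment during maintenance 2, the imputation model specified in the protocol is unstable", giving absurdly large imputed counts.

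Other relevant statements:

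- SAP 2.2: the "dispersion parameter in the negative binomial distribution is assumed to be 3.1", and "4% of subjects will withdraw before starting the maintenance period".
- SAP 2.4.1, backup rule: the Poisson imputation is abandoned if it cannot be fitted or would "inflate the standard error of the treatment ratio on logscale by more than 15" per cent relative to the analysis without imputation. The replacement is a negative binomial imputation model fitted to all on-treatment maintenance 2 data.
- SAP 2.1: "The primary and secondary endpoints will be tested in a hierarchical order using the on-treatment estimand". SAP 2.5.1 adds: "The hierarchical testing strategy will control the family wise type 1 error in the strong sense at 5% (two sided").
- SAP 2.4.2 includes an analysis restricted to observed data: "Subjects without on-treatment data for maintenance 2 period will be excluded from this analysis, and thus no imputation is needed".

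**The concern.** The imputation model contradicts the variance assumption used everywhere else in the plan. Two quantities are understated whenever the Poisson imputation is kept:

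1. The donor rate is estimated from a few over-dispersed subjects as if they were Poisson. Its posterior is too tight, so Rubin's between-imputation variance is too small.
2. The imputed counts lack subject-to-subject spread. They pull down the dispersion estimated in the final model, so the within-imputation standard error is too small as well.

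The 15% rule looks only for inflation, so it cannot detect a standard error that is too small. The error is anti-conservative, and it affects the test that decides superiority and opens the hierarchy.

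**Working it through.** **Inputs.** From SAP 2.2: 805 subjects per arm, 1.8 events per patient-year on IDeg, dispersion k = 3.1, and 4% of subjects without maintenance 2 data. From SAP 1.1: 36 weeks. The adjusted rate ratios in SAP Table 2–1 imply 6% rather than 4%: (0.765 − 0.75)/0.25 = (0.812 − 0.80)/0.20 = (0.718 − 0.70)/0.30 = 0.06. Both shares were therefore used (32 and 48 subjects per arm). The number of donors is not in the documents, so a range is shown.

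**Reproducing the stated power.** Var(log RR) = (1/μ₁ + 1/μ₀ + 2k)/n, with μ₁ = 1.8 × 36/52 = 1.246 and μ₀ = 1.246/0.765 = 1.629. This gives (0.802 + 0.614 + 6.2)/805 = 0.00946, SE 0.0973. Then |ln 0.765|/0.0973 − 1.96 = 0.794, so power is 78.6% (stated: 79%). The other eight cells of Table 2–1 also reproduce.

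**What the Poisson step leaves out.**

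- Variance of one imputed count: negative binomial 1.246 + 3.1 × 1.246² = 6.06; Poisson 1.246, about one fifth.
- Variance of the donor rate, with donor exposure uniform over 36 weeks (assumption): understated by a factor of about 1 + 3.1 × 1.246 × 2/3 = 3.6.

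**Type I error.** Three separately programmed simulations were run with RR = 1, gamma-Poisson counts and the SAP's 15% rule.

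- A: 4,000 trials per cell, 25 imputations, Monte Carlo error 0.3–0.4 points.
- B: 5,000–6,000 trials per cell, 50 imputations, similar error.
- C: 3,000 trials per cell, with the fallback approximated by the test without imputation.

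A and B fitted the donor model with dosing time and age. Overall two-sided error, fallback included:

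| Imputed | Donors per arm | A | B | C |
|---|---|---|---|---|
| 4% | 10 | 5.2% | 5.3% | – |
| 4% | 20 | 5.5% | 6.1% | 5.7% |
| 4% | 40 | 6.4% | 6.4% | 6.0% |
| 4% | 60 (A), 72 (B) | 7.0% | 6.5% | – |
| 6% | 10 | 5.6% | 5.5% | – |
| 6% | 20 | 7.4% | 6.1% | 8.3% |
| 6% | 40 | 7.3% | 6.8% | 7.0% |
| 6% | 60 (A), 72 (B) | 8.0% | 7.5% | – |

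Without imputation the error was 4.6–5.6% (A), 4.7–5.7% (B) and 5.0–5.6% (C). The 15% rule sent 68–75% (A) or 82–87% (B) of trials to the fallback with 10 donors, 12–16% or 23–27% with 20, and about 1% or fewer with 40 or more.

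**Standard errors.** At 6% imputed and 40 donors (A), the reported SE averaged 0.099, the true SD was 0.108 and the SE without imputation was 0.102. In 96% of those trials the imputed SE was below the no-imputation SE, and the median estimated dispersion was 2.85. As a check by hand, a test with true SD 0.108 and reported SE 0.099 rejects when |z| > 1.96 × 0.099/0.108 = 1.797, a two-sided error of 7.2% (simulated: 7.3%). In B, at 6% and 72 donors, the figures were 0.0974 against 0.1064, with a median ratio to the no-imputation SE of 0.948. The donors are already in the data set, so imputing from them cannot genuinely add precision.

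**Other endpoints.** Nocturnal episodes (0.55 per patient-year, 20–40 donors) gave 5.1–5.7%, not clearly above the 4.6–5.3% without imputation. For severe episodes (0.03 per patient-year), at least one arm's donors have no event in 97%, 89% and 79% of trials with 20, 40 and 60 donors, so the Poisson model would mostly not be used. The ITT estimand was not simulated.

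**The case against.** The strongest reply is that the donor count is constrained after all. SAP 3.7 calls it low and reports imputed counts in the millions or billions even from the simplest negative binomial model. A small simulation of that model (25 replicates per cell, normal priors with SD 10) produced a count above one million in about 95%, 92%, 44%, 8% and 0% of trials with 5, 10, 20, 40 and 60 donors per arm. That points to about 20 donors or fewer, and with 10 the 15% rule usually selects the fallback and the error stays near 5%. This stands: the 40–72 donor rows are the less likely ones. It does not remove the problem, because at 20 donors and 6% imputed the three simulations give 6.1–8.3%.

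That spread exceeds Monte Carlo error (A and B differ by 1.3 points, combined error about 0.5). It reflects priors and posterior computation that the SAP leaves unstated, so no single cell should be read to a decimal place.

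It can also be said that the no-imputation analysis in SAP 2.4.2 would expose a fragile result, since only borderline p-values would differ. That is true, but that analysis does not decide the claim.

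Finally, a better-calibrated donor model triggers the all-subject fallback more often, and so partly replaces the missing-data assumption it was meant to preserve. This is a real cost, quantified with the change below.

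**Conclusion.** The concern holds for the primary endpoint. The two-sided 5% test runs at about 5–8% under the plan's own rate, dispersion and 4–6% imputed share. There is no clear excess near 10 donors per arm, roughly 5.5–6% at 20 donors with 4% imputed, and roughly 6–8% in the remaining cells. Direction and mechanism are firm; the exact size is of medium confidence.

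The figures assume equal donor numbers in the two arms, uniform discontinuation times, no true age or dosing-time effect, and an analysis model simplified to treatment and exposure (in A). An imputed share above 6%, for instance through refusal to re-consent, would be expected to increase the error; this was not simulated. No claim is made for the nocturnal, severe or ITT analyses. This should be fixed, because the plan promises strong control at 5%.

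**What to change.** In SAP 2.4.1, replace the Poisson draw with a negative binomial (gamma-Poisson) draw:

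- Keep taking the rate from same-arm subjects who discontinued in maintenance 2.
- Fix the dispersion at the estimate from the negative binomial model already fitted, without imputation, for the 15% comparison. Compute the posterior of the donor rate under that dispersion. Dispersion is then no longer estimated from sparse donors, the weak point of the protocol's model.
- Keep the 15% rule and the existing fallback.
- State in advance whether the donor model keeps dosing time and age or uses one rate per arm.

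Across the eight scenarios of simulation A, the error returned to 4.4–5.6% with covariates and 4.3–5.6% with one rate per arm.

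The cost is SAP wording and a few lines of code, with no new data. The interval becomes about 0–10% wider. The fallback is used more often: with covariates, in 98–100% of trials with 10–20 donors per arm, 48–76% with 40 and 15–34% with 60; with one rate per arm, in 70–88% with 10, 20–49% with 20, 1–9% with 40 and about 1% or less with 60. If donors are as few as SAP 3.7 suggests, one rate per arm retains the discontinuer-based assumption more often.

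A second option is to make the all-subject negative binomial fallback the primary imputation model. It also gives about 5% (4.6–5.6% in A, 4.9–5.3% in B), but it replaces discontinuers with all on-treatment subjects and so changes the missing-data assumption.

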2.4.3 Statistical analysis for the ITT estimand

The ITT estimand will be estimated based on information from maintenance 2 collected regardless of whether subjects used randomised treatment or not, i.e. including data after premature discontinuation.

Missing data for withdrawn subjects prior to maintenance 2 will be imputed based on off-treatment data from the same arm from maintenance 2. The imputations and the analysis will be made using the same method as for the on-treatment estimand. If the imputation model cannot fit or leads to inflate the standard error of the treatment ratio on logscale by more than 15% compared to a negative binomial model fitted to the available on- and off-treatment data during maintenance 2 without any imputation the analysis will not be performed.

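### Does the primary negative binomial model need a term for hypoglycaemia history before randomisation?

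*SAP*

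**What the plan says.** SAP 2.1 introduces the model terms with "In the statistical models explanatory factors will be categorized as follows" and lists treatment, pre-trial OADs (0, 1, 2 or more), region, sex and dosing time. SAP 2.4.1 uses that list for the primary endpoint: the ratio is "estimated using a negative binomial model with all the factors described in section 2.1, age as covariate and log exposure time as offset". Subjects who stop before maintenance 2 have their counts imputed from "a Bayes Poisson log-link model dosing time as a factor, age as covariate", again without history. A fallback applies if this imputation "leads to inflate the standard error of the treatment ratio on logscale by more than 15" per cent.

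Other hypoglycaemia analyses borrow the method. SAP 2.4.3 states for the ITT estimand that "the analysis will be made using the same method as for the on-treatment estimand", and SAP 2.5.1 states "The hypoglycaemic endpoints will be analysed with the same analysis method as the primary endpoint".

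On power, SAP 2.2 concludes "The power equals 79% with the number of randomised subjects and the assumptions above", having assumed that "4% of subjects will withdraw before starting the maintenance period".

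On history, Protocol v3.0 section 6.2 requires at least one of criteria 3a to 3e and aims for at least 80% of subjects with 3e (hypoglycaemia in the 12 weeks before screening). The Baseline Hypo Questionnaire (8.1.1, 8.6) and one awareness question (8.2.3) are completed at screening.

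**The concern.** Past hypoglycaemia is a natural candidate predictor of future hypoglycaemia, and this trial selects for it. The insulin-dose analysis in SAP 2.5.1 adjusts for the logarithm of pre-trial dose, which is a baseline version of its own outcome. The hypoglycaemia model has no counterpart, and no sensitivity analysis in SAP 2.4.2 supplies one. Planned power is just under 80% and the assumed dispersion is large (3.1). Explaining part of that dispersion with a variable that may already be on file looks like power available at almost no cost. If the gain were several points, leaving it out of a confirmatory analysis would deserve comment.

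**Working it through.** **1. Bias.** Allocation is randomised, and Protocol section 11 describes no stratification on hypoglycaemia history, so no stratification factor is missing from the model. With a log link the rate ratio is the same quantity whether or not an independent baseline factor is in the model. Simulated mean log ratios without and with the term agree: -0.2667 and -0.2669 (complete data, history ratio 1.5); -0.2853 and -0.2860 (planned imputation, history ratio 2).

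**2. The plan's own figure.** Inputs from SAP 2.2: 805 per arm, IDeg rate 1.8 per year, dispersion k = 3.1, adjusted ratio 0.765. From SAP 1.1: t = 36/52 years.

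n·Var(log RR) = 1/(t·1.8) + 1/(t·1.8/0.765) + 2k = 0.802 + 0.614 + 6.2 = 7.616

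SE = √(7.616/805) = 0.0973; 0.2679/0.0973 − 1.96 = 0.794; power 78.6%, which matches the stated 79%.

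**3. A yardstick.** The tabled ratio implies (0.765 − 0.75)/(1 − 0.75) = 6% early withdrawal. The text's 4% gives 0.96 × 0.75 + 0.04 = 0.76 and power 80.6%. The plan's own inputs therefore leave about 2 points open. That mismatch is a separate matter and serves here only as a scale.

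**4. Dispersion that history could explain.** The documents give no prognostic strength, so the history rate ratio R is assumed. Holding total heterogeneity at 3.1 with a share p of subjects meeting 3e,

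k′ = 4.1/(1 + CV²) − 1.

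For p = 0.8 and R = 2: mean 0.2 + 0.8·2 = 1.8, mean square 0.2 + 0.8·4 = 3.4, 1 + CV² = 3.4/3.24 = 1.0494, k′ = 2.907. R = 1.5 gives 3.018; R = 4 gives 2.646.

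**5. Gain in power by simulation.** 20,000 trials per case at ratio 0.765. The imputation runs assume 6% per arm stop before maintenance 2 and 5% during it, with 20 imputations and the 15% rule. Gains were taken before rounding.

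| 3e share | R | Complete data | Gain | Planned imputation and 15% rule | Gain |
|---|---|---|---|---|---|
| 80% | 1.5 | 78.4 to 78.9% | 0.5 | 76.5 to 76.7% | 0.3 |
| 80% | 2 | 78.6 to 79.4% | 0.8 | 76.8 to 77.2% | 0.5 |
| 80% | 4 | 78.3 to 80.8% | 2.5 | 76.3 to 77.6% | 1.3 |
| 90% | 2 | 78.7 to 79.0% | 0.4 | 76.8 to 77.1% | 0.3 |

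The Monte Carlo SE of a gain is 0.11 to 0.18 points. Before the 15% rule is applied, the imputation gains are 0.2, 0.5, 1.3 and 0.3. If 9% stop during maintenance 2, they are 0.7 (R = 2) and 1.3 (R = 4). Imputed counts carry no history signal, which roughly halves the benefit at R = 4. For weaker history the gain runs towards zero: about 0.1 points at R = 1.2 on complete data.

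**6. Cross-check by standard errors.** In separate runs with 6% imputed, the SE with the term was 0.998 (R = 1.5) and 0.996 (R = 2) of the SE without it. With 0.2679/0.0973 = 2.754, 2.754/0.998 − 1.96 = 0.800 gives 78.8%, and 2.754/0.996 − 1.96 = 0.805 gives 79.0%: gains of about 0.2 and 0.3 points. With 4% imputed the gains are about 0.2 to 0.6. A closed-form calculation on complete data is more generous, at 0.7 (R = 1.5) and 1.6 (R = 2), still under 2 points.

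**7. Type I error.** On complete data it moves from 5.2 to 5.0% (R = 2) and from 5.1 to 4.9% (R = 4) when the term is added. With imputation and the rule it moves from 7.3 to 7.1% and from 7.3 to 7.4%. The excess over 5% comes from the imputation step, is present in both models, and has nothing to do with history.

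**The case for a change.** The best case for the term is that it is cheap. Criterion 3e is probably known for each subject, since the 80% aim could not otherwise be checked. One prespecified binary term, added while still blinded, does no harm. SAP 3.0 itself made late changes to the primary analysis (SAP 3.7, 3.9), so one more would not be out of character. A more evenly split history variable could also do better: at 20 to 50% prevalence and R = 2, the gain under imputation is about 0.75 points by standard errors, and simulated rejection rates differed by 1.4 to 1.75 points (Monte Carlo SE about 0.6).

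Some of this stands. Adjusting for a strong prognostic factor is good practice, and a sponsor who had listed one at the outset would have done nothing wrong. Three things keep it from being a fault in the plan.

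- **The variable is not established.** Criterion 3 needs only one of 3a to 3e, so a subject admitted under 3d need not have 3e recorded, and the 80% is an aim. The questionnaire and the awareness item are shown to be collected, but the documents do not show that either predicts the endpoint.
- **3e is probably a weak predictor.** Subjects without it must meet one of the other risk criteria, 3a to 3d. It accepts symptoms alone or glucose up to 3.9 mmol/L, whereas the endpoint needs a value below 3.1 mmol/L with symptoms, or a severe episode (SAP 2.7).
- **The change is not free.** The factor list has been the same in Protocol v2.0 and v3.0 section 17.1 and in SAP 2.1. Reopening the primary model of a final SAP (12 March 2019) in an open-label trial invites questions about its motive. It would also mean editing the 15% comparator, SAP 2.4.3 and SAP 2.5.1. The severe endpoint, with about 805 × 36/52 × 0.03 = 17 expected IDeg events, would have to carry the extra term or be analysed differently from the other two.

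**Conclusion.** The concern does not hold. The model in SAP 2.4.1 is prespecified, unbiased with respect to this omission, and consistent with SAP 2.1. The forgone precision is about 0.2 to 0.5 power points under the planned imputation if 80% meet 3e and R is 1.5 to 2, about 1.3 at R = 4, and close to zero if 3e predicts weakly. These figures rest on an assumed R, an assumed 5% stopping during maintenance 2, and the dispersion of 3.1 in SAP 2.2. Under the planned imputation, every 3e case examined stays below the 2 points left open by the 4% and 6% withdrawal readings. Reasonable statisticians could choose either model, and nothing in the plan has to be corrected. The conclusion covers the choice of covariates only. It does not vouch for the assumption that early discontinuers resemble those who stop in maintenance 2, or for the behaviour of the Poisson imputation.
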